### 3 Study design

#### 3.1 Primary, secondary and additional study designs

**Figure 1. Diagram of sample size by cohort and study arm**

- 3.1.1 **Primary study (PA1-2, SA3, SA5):** The primary study is a multi-site cluster RCT comparing GBC with GBC+PIPT for patients with acute LBP deemed to be high risk for transition to chronic LBP (RCT cohort). Data collection will be conducted at baseline, 6 months, and 12 months. Resource use, determined with EMR data, will be evaluated in a subset of patients.
- 3.1.2 **Secondary study (SA4-5):** A secondary ancillary prospective, observational cohort study will be conducted for those patients presenting with acute LBP

deemed to be low or medium risk. Patients with acute LBP who do not meet criteria for high risk will be identified for the prospective observational cohort. These patients will receive GBC and not be targeted with any specific study interventions, such as PIPT. Data collection will also occur at baseline, 6 months, and 12 months. The objective of this ancillary observational study is to precisely determine the rates of transition from acute to chronic LBP and resource use in the treatment of LBP.

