### 5.1 Interventions, administration, and duration

5.1.1 **Referral to PIPT:** As a result of the QI initiative, all patients in the intervention arm identified as high risk will be referred to PIPT. PCPs will have the results of the screening questionnaires in the EMR to identify the high risk acute LBP patients and refer them to PIPT. PCPs will provide patient education materials as appropriate, including materials about musculoskeletal injury, PT, and pain management. Referrals will occur through automatic electronic referral, manual electronic referral, written prescription, fax, or verbal means.

5.1.2 **Delivery of PIPT:** Upon referral to PIPT, trained physical therapists will use the PIPT approach with the high risk patients. The number of PT sessions recommended by the physical therapist will be based on their clinical judgment. Physical therapists will complete a checklist based on PT standards of care (see Appendix 4 based on Guide to Physical Therapy Practice <http://guidetoptpractice.apta.org/>) that will reflect the elements of the treatment provided. This checklist will be sent to the PCP and entered into the EMR. This

checklist will allow tracking of how many patients have received the prescribed physical therapy (i.e., a completed checklist, number of PT sessions).

- 5.1.3 **Patient-centered PIPT discharge instructions:** Community discussions with patients emphasized the desire to have a home exercise program in place after physical therapy that is feasible, effective, and sustainable. As an adjunct to the PIPT program, physical therapists can provide patients at discharge printed instructions for home practice exercises and a list of recommended community-based exercise classes and resources appropriate for the patient.
- 5.1.4 **Patient-reported outcomes:** At 6 months for all sites, lists of eligible patients will be generated from the EMR and patients will be contacted by research assistants by phone, email, or postal mail. This procedure is a modest departure from the pragmatic approach (PRECIS-2 follow-up domain); however, stakeholders indicated that 6-month assessments of this nature were not normal practice for the PCP clinics. These assessments will be for the Chronic LBP Questionnaire and Oswestry.

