## 6 Study procedures

### 6.1 Schedule of evaluations

**Table 2: Schedule of evaluations**

| Assessment                    | Screening and Enrollment | 6-Months | 12-Months |
|-------------------------------|--------------------------|----------|-----------|
| Chronic LBP Questionnaire     | ✓                        | ✓        |           |
| STarT Back Tool               | ✓                        |          |           |
| Oswestry LBP Disability Index | ✓                        | ✓        |           |
| EMR Medical Resource Use*     |                          |          | ✓         |

*\*EMR data for UPMC, BMC, JHM, IH*

A detailed flow diagram for each regional site is provided in Appendix 5.

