- A total sample size of at least 8,760 participants is needed from these sites to meet the aims of the study,
- The study needs to be conducted within the clinical setting (i.e., a pragmatic trial), which typically allows <15 minutes per patient visit; the consent/authorization procedures would disrupt the clinical setting and potentially impact patient care.

6.2.3 **Enrollment and baseline evaluation:** Upon determination of eligibility, patients will be enrolled in the QI initiative of the study. Baseline data will be contained in the EMR and extracted for study purposes, including screening results, demographic information, billing information, and clinical data (e.g., diagnoses, referrals to specialists). Patients identified as high risk, acute LBP patients in the intervention arm will be referred to PIPT, and this referral will also be captured in the EMR. The list of baseline variables to be extracted from the EMR is provided in Appendix 6.

6.2.4 **Randomization:** As a cluster RCT, randomization will occur at the clinic level and not the patient level; therefore, randomization is not a factor in the enrollment or baseline evaluation.

6.2.5 **Follow-up:** Follow-up to the initial screening and QI enrollment visit will occur through three mechanisms:

- 1) **Referral to PIPT:** For eligible patients referred to PIPT, follow up at PT will be evaluated through the checklist completed at the PT visit and returned to the PCP site. This checklist will indicate use of the PIPT approach and number of PT sessions.
- 2) **Six-month assessment:** Research staff will contact all enrolled patients 6 months after their initial visit at all sites and conduct the Chronic LBP Questionnaire and the Oswestry to assess the primary outcomes.
- 3) **Medical resource utilization:** Researchers will also extract data from the EMR at select sites to determine the secondary outcome of LBP-related medical resource utilization of tests, procedures, and pharmaceuticals by enrolled patients for 12 months after the initial visit.

The list of variables for medical resource utilization is provided in Appendix 6.

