## 9.5 Data analyses

- 9.5.1 **Primary outcome 1:** This initial analysis (**PA1**) will use a generalized linear mixed model with a logit link controlling for block set (see Randomization) and a fixed effect for intervention accounting for the cluster RCT design with a random clinic effect. Primary analyses will also adjust for patient characteristics (maladaptive pain coping behaviors such as catastrophizing and fear avoidance, functional impairment as measured by the Oswestry, and presence

of psychiatric comorbidities), as these have been associated with higher transition to chronic LBP. The intraclass correlation coefficients will also be estimated and reported for all outcome measures to assess the assumptions for sample size analyses and also for future investigations using similar designs and outcomes. Analysis for the secondary aims (**SA4** and **SA5**) will be largely descriptive assessing the proportion of patients who transition to chronic LBP among the low and moderate risk observational cohort. The proportion and confidence interval will be estimated using generalized linear models adjusting for clustering.

- 9.5.2 **Primary outcome 2:** This aim (**PA1**) will be analyzed using contrasts from a linear mixed models analysis for 6-month back-related function (Oswestry) controlling for baseline Oswestry and the block set (see Randomization). The intervention will first be explored by time interaction, and then proceed to a main effects model with only group and time. For the secondary aims (**SA4** and **SA5**) patient-centered outcomes, such as functional status, would use general linear models if deemed appropriate based on normality assumptions. If normality is hugely violated, a cutpoint for 'response' will be applied.

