- 9.5.3 **Secondary outcome:** Analyses of health care utilization data (**SA3**) will use generalized linear mixed models with the distribution determined by the type of data but still controlling for the cluster randomized trial design by having random effects for clinics. Logit link (binary distribution) will be used for health care outcomes, such as surgery, that are dichotomous (Yes/No) variables. For outcomes resulting in count data over the time frame such as number of outpatient visits for back pain, hospitalizations or ER visits, Poisson or negative binomial distribution with log link will be used to compare the event rates controlling for the period of follow up. The secondary aims (**SA4** and **SA5**) would use a similar approach.

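### Section 9.5.2 gives two instructions for the Oswestry primary outcome (PA2) that do not fit together: a baseline-adjusted 6-month model, and a group-by-time step leading to a group-plus-time model

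*Combined protocol and SAP*

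**What the plan says.** Section 9.5.2 covers the second primary outcome. Its first sentence specifies contrasts from a "linear mixed models analysis for 6-month back-related function (Oswestry) controlling for baseline Oswestry and the block set". Its second sentence reads: "The intervention will first be explored by time interaction, and then proceed to a main effects model with only group and time". The second sentence mentions neither baseline nor block set, gives no rule for moving from one step to the next, and is not marked as supportive. The paragraph labels the aim PA1 where PA2 is meant.

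The comparison itself is described elsewhere. Section 1.1.3 compares the arms on the Oswestry at 6 months. Sections 9.1.6 and 9.4.2 describe it as change in score from baseline to 6 months.

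On timing, Table 2 ticks the row "Oswestry LBP Disability Index" at screening/enrollment and at 6 months and leaves 12 months blank. Section 5.1.4, on the 6-month contact, says: "These assessments will be for the Chronic LBP Questionnaire and Oswestry". Section 6.2.5 has research staff "contact all enrolled patients 6 months after their initial visit at all sites and conduct the Chronic LBP Questionnaire and the Oswestry". Section 3.1.1 says more generally: "Data collection will be conducted at baseline, 6 months, and 12 months". The only 12-month item in Table 2 and 6.2.5 is EMR resource use.

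On clustering, 9.5.1 specifies "a fixed effect for intervention accounting for the cluster RCT design with a random clinic effect", and 9.5.3 describes its models as "still controlling for the cluster randomized trial design by having random effects for clinics". The PA2 sentence in 9.5.2 says only that the model is a linear mixed model.

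**The concern.** A primary estimate and p-value should come from one model named in advance. Here the paragraph starts with one model and ends on another, and nothing says which of them yields the PA2 result.

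The language of the second sentence (an interaction with time, then main effects of group and time) belongs to a repeated-measures analysis with at least two modelled time points. The schedule supplies one post-baseline Oswestry. An analyst can make the time terms estimable only by treating baseline as an outcome, which sets aside the baseline adjustment of the first sentence. The model that the paragraph then ends on omits the term that holds the difference in change. Two analysts following the same paragraph could report different results for a primary outcome.

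**Working it through.** **Inputs.** Oswestry times: baseline and 6 months (Table 2, 5.1.4, 6.2.5). Enrolment of 1,860 and 40% non-response at 6 months (9.2.2), so 1,860 × 0.6 = 1,116 six-month scores. ICC 0.05 (9.2.3, given for PA1). The documents give no Oswestry SD, within-patient correlation, target effect or power, so there is no PA2 figure of the plan's own to reproduce. Assumed: within-patient correlation ρ of 0.2-0.7, equal SDs at first, and no expected arm difference at baseline because clinics are randomized.

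**Reading A: baseline as covariate (first sentence).** Every outcome row is at 6 months, so time is constant.
- Intercept, arm, baseline: 3 columns, rank 3.
- Adding time: 4 columns, rank 3.
- Adding time and arm × time: 5 columns, rank 3.

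Neither time term is estimable. Without them the model has full rank, and the arm coefficient carries 1.00 of the 6-month effect. It also answers the change comparison of 9.1.6 and 9.4.2. If Y = a + d·arm + b·B, where B is baseline, then Y − B = a + d·arm + (b − 1)·B, with the same d.

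**Reading B: baseline stacked as an outcome row.** Intercept, group and time now have full rank (3 of 3). The difference in change is group × time, which this model leaves out. The remaining group coefficient is a weighted average of the baseline arm difference (expected 0) and the 6-month arm difference d. With equal SDs and a fraction c of patients having a 6-month score (baseline-only rows kept), the GLS weights are:
- baseline ∝ c/(1 + ρ) + (1 − c)
- 6 months ∝ c/(1 + ρ)

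The share of d carried is therefore 1 / [(1 − ρ) + (1 + ρ)/c].

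| | ρ = 0.2 | 0.3 | 0.5 | 0.7 |
|---|---|---|---|---|
| Complete pairs, c = 1 | 0.500 | 0.500 | 0.500 | 0.500 |
| c = 0.6 | 0.357 | 0.349 | 0.333 | 0.319 |

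Example at c = 0.6, ρ = 0.2: 1/(0.8 + 1.2/0.6) = 1/2.8 = 0.357.

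**Clustering.** With a clinic intercept shared by both visits, ICC 0.05 and 60 clinics of 31 patients (18 or 19 completers each), exact GLS gives 0.500 in complete pairs and 0.361, 0.352, 0.335 and 0.320 at 60% response. The shares hardly move.

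**Sensitivity to the SD ratio.** Let r be the 6-month SD divided by the baseline SD. In complete pairs, ignoring clustering, the share is (1 − ρr)/(1 + r² − 2ρr).
- r = 0.8: 0.84/1.32 = 0.64 at ρ = 0.2, and 0.44/0.52 = 0.85 at ρ = 0.7.
- r = 1.25: 0.75/2.0625 = 0.36 at ρ = 0.2, and 0.125/0.8125 = 0.15 at ρ = 0.7.

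**Simulation check.** Sixty replicates used 60 clinics with 18 completers each and illustrative values: true effect −5, SD 17, correlation 0.4, ICC 0.05. Mean estimates were −4.90 for the baseline-adjusted 6-month model, −4.88 for group × time, and −2.48 for the group term of the group-plus-time model. The last is −2.48/−5 = 0.50 of the true effect.

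**The case against.** The strongest reply is that the first sentence of 9.5.2 is already a complete, usable model and governs, while the second is described as exploration. That stands in large part. An analyst who keeps baseline as a covariate will find that time drops out and will be left with the right arm estimate. Nothing forces baseline into an outcome row, and 1.1.3, 9.1.6 and 9.4.2 all point away from the group coefficient of a group-plus-time model. The reply does not remove the conflict. The exploratory wording attaches to the interaction step, the main-effects model reads as the destination, and the sentence sits unmarked in the primary-analysis paragraph.

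A second reply is that a 12-month Oswestry was once intended. Section 3.1.1 mentions 12-month data collection, and Appendix 6 lists contact details for 6- and 12-month assessments. With two post-baseline visits and baseline as a covariate, the sentence would be coherent. This suggests leftover text but does not prove it, and it does not rescue the sentence: no 12-month Oswestry is scheduled.

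A third reply is that a clinic effect is implied by the term mixed model, by 3.2, which makes the cluster the unit of randomization and analysis, and by the promise in 9.5.1 to report ICCs for all outcome measures. That is fair. Naming the effect in 9.5.2 is tidying.

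A reader might infer that the plan makes the PA2 treatment effect inestimable, or that the trial will halve it and lose power. The documents support neither. On the first-sentence reading only the time terms fail. Attenuation arises only on the stacked reading, which the plan's own endpoint descriptions disfavour. Any power loss would need an Oswestry SD, correlation and target effect that the documents do not give, so none is claimed here.

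**Conclusion.** The point holds as an inconsistency in the confirmatory specification of a primary outcome. The second instruction is wrong as written, because it matches the scheduled data on neither reading. With baseline as a covariate it asks for terms that cannot be estimated. With baseline as an outcome it ends on a model without the term that carries the stated comparison. This conclusion rests on the text and the schedule alone and needs no numerical assumption.

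The size is conditional. Following the first sentence loses nothing. On the stacked reading only, with equal SDs and a correlation of 0.2-0.7, the group coefficient carries 0.50 of the 6-month effect in complete pairs and 0.32-0.36 at 60% response. SD ratios of 0.8 to 1.25 move the complete-pairs share anywhere from 0.85 to 0.15, so these figures illustrate the problem and do not forecast a bias. PA1, which sets the sample size, is not affected.

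**What to change.** In 9.5.2:
1. Delete the sentence on the time interaction and the main-effects model.
2. State that the PA2 estimate and p-value are the arm coefficient from one linear mixed model of 6-month Oswestry on arm, baseline Oswestry and block set, with a random clinic effect and no time term.
3. Correct the PA1 label to PA2 (clerical).

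Sections 9.1.6 and 9.4.2 can stay as they are, because with baseline adjusted the change score and the 6-month score give the same arm coefficient.

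The cost is wording only: one sentence deleted, one added, one label corrected. No new data are needed, and neither the sample size nor trial conduct changes.

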### 9.3 Randomization, sample size and power – observational cohort

- 9.3.1 **Randomization** is not applicable to the observational cohort because moderate and low risk patients will not receive the PIPT intervention.
- 9.3.2 **Sample size** is again based on a total of 60 PCP clinics. An average of n=115 patients will be enrolled per clinic, for a total sample of N=6,900 low or medium risk acute LBP patients.
- 9.3.3 **Power:** The sample size will allow precise determination of 1) the transition rates for low risk and medium risk acute LBP who receive GBC; 2) differences between low/medium risk patients receiving GBC in the observational cohort and high risk patients receiving GBC in the intervention group; and most importantly, 3) differences among low/medium risk patients due to specific subgroup characteristics, in particular patients who are underserved, obese, depressed, or smokers. Of the three objectives, the subgroup analyses require the greatest sample size, and therefore will be described in detail here.

For the purposes of the calculations, from the literature it is assumed that low and medium risk subjects with acute LBP have an expected 20% transition to chronic. Data on obesity and smoking rates are based on national surveys. Depression rates are based on prevalence rates reported in primary care. Proportions of underserved patients are estimated from patient registries at each of the five regional sites. For the underserved, obesity, and smoking subgroups, the given sample sizes in Table 3 would be ample enough to detect at least a 30% relative difference (6% absolute difference) from 20% with powers ranging from 79% to 87%. The study would have 65% power to detect a 40% relative or 8% absolute difference (hypothesized increased rate of transition) for the depression subgroup.

**Table 3: Power** at a significance level of 0.05 to detect the specified % absolute and relative differences from a 20% chronic transition rate based on a two-sided Z-test adjusted for clustering within clinic (ICC=0.01) among 60 clinics, N=6900 enrolled and conservatively 60% response rate at 6 months in the low or medium risk population (adjusting for design effect and nonresponse N=2464).

| Subgroups (N)               | 25% relative difference
(5% absolute difference) | 30% relative difference
(6% absolute difference) | 35% relative difference
(7% absolute difference) | 40% relative difference
(8% absolute difference) |

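### Section 9.5.2 models the SA4/SA5 Oswestry outcomes without any adjustment for clinic, so intervals for low/medium-risk means and between-arm contrasts would be too narrow

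*Combined protocol and SAP*

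**What the plan says.** Section 9.5 covers three families of outcomes.

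- **Transition to chronic LBP (9.5.1).** PA1 has a random clinic effect. For the low/medium-risk cohort, "The proportion and confidence interval will be estimated using generalized linear models adjusting for clustering".
- **Resource use (9.5.3).** The SA3 models are described as "still controlling for the cluster randomized trial design by having random effects for clinics", and SA4/SA5 are to follow a similar approach.
- **Oswestry (9.5.2).** PA2 uses a "linear mixed models analysis for 6-month back-related function (Oswestry) controlling for baseline Oswestry and the block set", without saying which random effects are fitted. For SA4/SA5, "patient-centered outcomes, such as functional status, would use general linear models if deemed appropriate based on normality assumptions". If normality fails badly, the score is to be cut into response or no response. Neither SA4/SA5 option mentions clinic.

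The power section for the same low/medium-risk cohort does allow for clinic: Table 3 is "based on a two-sided Z-test adjusted for clustering within clinic (ICC=0.01) among 60 clinics, N=6900 enrolled and conservatively 60% response rate at 6 months", which it reduces to an effective size ("adjusting for design effect and nonresponse N=2464"). Section 9.4.2 plans the Oswestry comparison between intervention and comparator clinics in low/medium-risk patients and in subgroups, as well as in high-risk patients.

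**The concern.** A general linear model in its ordinary sense treats patients as independent. Patients at one clinic share clinicians, case mix and local practice, so their scores are likely to be correlated. A mean over the whole cohort, or a difference between arms, then carries between-clinic variance that this model leaves out of its standard error. The choice in 9.5.2 turns on normality alone, and normality has no bearing on clustering.

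The affected quantities are planned results. SA4 reports functional outcomes at 6 months in the observational cohort, and Section 3.1.2 gives precise estimation as that cohort's purpose, although it names transition rates and resource use there. H5 concerns the arm effect within subgroups, which is a comparison between clinics. An analyst who follows 9.5.2 to the letter would report Oswestry intervals that are too tight, beside transition intervals for the same patients that are properly adjusted.

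**Working it through.** **Inputs from the plan (Section 9.3 and Table 3).** "An average of n=115 patients will be enrolled per clinic, for a total sample of N=6,900 low or medium risk acute LBP patients"; 60 clinics; 60% response at 6 months; ICC 0.01; two-sided 0.05 level.

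**Step 1: reproduce the plan's own figure.**
- Responders: 6,900 × 0.60 = 4,140.
- Responders per clinic: m = 4,140 / 60 = 69.
- Design effect for equal clinic sizes: DE = 1 + (m − 1) × ICC = 1 + 68 × 0.01 = 1.68.
- Effective size: 4,140 / 1.68 = 2,464.3, which matches the plan's 2,464.

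The plan therefore accepts a design effect of 1.68 in this cohort. All 16 powers in Table 3 also reproduce within one point from that effective size, using a two-sided Z-test with unpooled variance.

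**Step 2: the effect of omitting clinic.** For a cohort mean or an arm contrast, the unadjusted standard error is too small by a factor √DE. The true coverage of a nominal 95% interval is 2Φ(1.96/√DE) − 1.

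The documents give no ICC for the Oswestry. The 0.01 is stated for the binary transition outcome in this cohort; using it for the Oswestry is an assumption, so a range is shown.

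| Assumed ICC | DE = 1 + 68 × ICC | √DE | Coverage |
|---|---|---|---|
| 0.005 | 1.34 | 1.16 | 91% |
| 0.01 (plan, binary outcome) | 1.68 | 1.30 | 87% |
| 0.02 | 2.36 | 1.54 | 80% |

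At ICC 0.01 the corresponding two-sided error rate is about 13%. Equal clinic sizes are the favourable case. If the coefficient of variation of 0.65 that Section 9.2.2 assumes for the RCT cohort also held here, DE = 1 + ((1 + 0.65²) × 69 − 1) × 0.01 = 1.97 and coverage would be about 84%.

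**Step 3: check by simulation.** 60 clinics of 69 patients, ICC 0.01, 4,000 runs, unadjusted analysis. Coverage of the nominal 95% interval was:
- cohort mean: 87%
- arm contrast: 87%
- contrast between patient subgroups mixed within every clinic: 95%

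The last result is expected, because the clinic effect largely cancels when both subgroups are present in each clinic. A characteristic concentrated in certain clinics, as insurance status may be, would lie between the two cases.

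**Step 4: arm effects within subgroups.** These are contrasts between clinics, but fewer patients per clinic contribute. With the subgroup shares in Table 3, an even spread over clinics and ICC 0.01:
- Underserved: 69 × 665/2,464 = 18.6 per clinic; DE = 1 + 17.6 × 0.01 = 1.18; coverage about 93%.
- Depression: 69 × 184/2,464 = 5.2 per clinic; DE = 1 + 4.2 × 0.01 = 1.04; coverage between 94% and 95%.

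**The case against.** The best defence is that this is a drafting omission. Section 3.2 makes the cluster the unit of randomization and analysis, 9.5.1 promises ICCs for all outcome measures, and clustering is handled for the same cohort in 9.5.1, 9.5.3 and Table 3. The secondary aims are also called largely descriptive. An experienced analyst might well add the clinic term unprompted. That may explain the gap, but it does not close it: the model named for SA4/SA5 has no clinic term, and the adjustment written for the binary outcome one paragraph earlier is absent here.

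The defence succeeds against three stronger readings that a reader might infer.

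1. **That PA2 has an inflated type I error.** PA2 is specified as a linear mixed model. Table 2 schedules the Oswestry only at baseline and 6 months, so with baseline as a covariate each patient contributes one outcome and a patient random effect could not be separated from the residual. Clinic is then the natural random effect, and Section 3.2 and the promised ICCs point the same way. The later mention of time is awkward and leaves the structure unspecified. Even if a patient-only repeated-measures model were fitted, a stable clinic effect would cancel from the group-by-time contrast. Any inflation of that contrast would depend on a clinic-by-time variance that the documents do not give.
2. **That SA4 coverage falls to about 65%.** That needs an ICC of 0.05 (DE = 1 + 68 × 0.05 = 4.40). The plan uses 0.05 for the RCT cohort, in the power calculation for the binary outcome, and calls it an upper bound. For the observational cohort it uses 0.01.
3. **That every SA5 interval is too narrow.** Contrasts between patient subgroups that vary within clinic are hardly affected, and Section 9.3.3 ranks subgroup differences as the observational cohort's most important objective.

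**Conclusion.** Wrong as written, for SA4/SA5 only. The stated Oswestry model ignores the clinic clustering that the plan allows for elsewhere in the same cohort. For low/medium-risk means and between-arm contrasts, a nominal 95% interval would cover about 87%. This rests on 69 completers per clinic, equal clinic sizes and an Oswestry ICC of 0.01 borrowed from the binary outcome. Arm effects within subgroups are affected to a lesser degree.

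For PA2 the random-effect structure is merely unspecified. The documents do not show that its intervals are too narrow or its test anti-conservative.

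**What to change.** In Section 9.5.2:

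- **SA4/SA5 Oswestry:** replace the general linear model with a linear mixed model with a random clinic intercept, or GEE with clinic-robust standard errors.
- **Cutpoint fallback:** apply the same clinic adjustment to the binary response, in line with 9.5.1.
- **PA2, as a clarification only:** state that the linear mixed model includes a random clinic intercept. The sentence labels this aim PA1, and the label can be corrected at the same time.

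The cost is a few sentences before analysis, with no new data and no change of design. The SA4 intervals for means and arm contrasts become about 1.3 times as wide at an ICC of 0.01, which is their correct width under that assumption.
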